After consenting, participants will complete a survey on a research laptop or on their own laptop at home (ThinkPad or MacBook air) computer (e.g. NHANES: SES [income, education], diet behavior and nutrition, physical activity and physical fitness, smoking and tobacco use; digital data use [Pew questionnaire]). Survey questions and citations are attached. For in-person enrollment, the survey will be collected on an incognito browser, <https://donate.centerfordigitalhealth.upenn.edu>. The data collection platform was reviewed by Penn Medicine IS team. After they complete the survey, they will be asked to donate their social media and digital data on the ThinkPad laptop computer or their personal laptop computer using the same browser and url. All data extraction will be consistent with the terms of service of the digital platform. Any social media posts collected on Facebook, Instagram or other social media platforms will not be linked to the participant's name. A unique code links the participant's survey responses to the de-identified social media posts. All data will be kept in a protected field in a password-protected database. All participants will receive a unique ID to track survey responses. Participants will receive a copy of consent-related documents as well as detailed information about what data are being extracted, how those data will be used and shared among the research team and instructions on how to permanently delete any study apps that provide ongoing access. The study team will not communicate with participants via social media or publicly post that the participant is involved in the study. The study team will not have the ability to post any messages or content on behalf of the user. We received clearance from the Office of Clinical Research to not collect participants' Social Security Numbers, since compensation is \$50. After the patient has completed enrollment, we will send them a follow-up summary about the status of the study (ie. how many participants are enrolled and the number of different data sources shared. After participants completed enrollment, we will re-contact participants to complete a short survey as related to objective 1. The study instrument will include questions related to health status, social media phenotypes, and AI perceptions, and patient activation. In addition to the above cohort, we offer the opportunity for survey respondents to enroll in a short interview (20-30 minutes) that will evaluate perceptions about use and engagement phenotypes, details about individual use of social media platforms, concerns and ways to mitigate concerns about phenotyping, potential uses of phenotypes, opportunities for patient centered design and implementation. Interviews will occur over 20-30 min in subgroups of 15-20 patients. Patients will consent to participate, and participation will be anonymous. Interviews will occur via virtual conference call and audio-recorded.

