
Study duration

It will take approximately 15-60 minutes during one session, but could take up to a week or more depending on completion of all enrollment steps for a participant to complete the study. For remote enrollment, it could take up to a week or more for participants to complete the eligibility survey, baseline survey, and share their digital data. If there are technical difficulties with our data collection application, we will ask participants who are opting to share Instagram if we can record their Instagram username for manual data extraction. Additionally, we will reach back out to them at a later time to share through our data collection application if there were any technical difficulties. All recruitment and follow up emails will be A/B tested, also known as split testing, the process of comparing two identical versions of an email. Potential variations include the order of information, email headers, and signatures. We aim to recruit 1000 participants over 4 years. Additionally, participants who agree to participate in the optional survey and interview will have to wait until a date and time is determined for the focus group to occur. Follow-up is necessary in this case.

Resources necessary for human research protection

Describe research staff and justify that the staff are adequate in number and qualifications to conduct the research. Describe how you will ensure that all staff assisting with the research are adequately

informed about the protocol and their research related duties. Please allow adequate time for the researchers to conduct and complete the research. Please confirm that there are adequate facilities for the research.

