discussions. We will specifically focus on words and words associated with previously identified predictors of CHD (e.g. demographics, family history, lifestyle, comorbidities, blood pressure) as identified in a systematic review of prediction models for cardiovascular risk by Damen et al. *BMJ* 2016. We will create classifiers to determine if a given instance of a disease term is referring to the disease or something unrelated (e.g. "If I see a celebrity I will have a heart attack" vs. "I am having chest pain, SOB and had a prior heart attack"). Our prior work has demonstrated that, as one might guess, some CV diseases, like "hypertension", are almost always used in their medical context while others, like "heart attack", are often used colloquially. We will also create classifiers to categorize language by broad grouping such as risk factors, treatment, medication adherence, symptoms, and by more granular categories such as active/sedentary, healthy food/unhealthy food, smoking. We will compare the performance of several machine-learning algorithms (e.g. support vector machines, random forests, and, in cases with adequate data, deep learning) and assess the accuracy of our disease term classifier against hand-annotated data. For multiword phrases we will use approaches for determining the probability that words occur together (e.g., pointwise mutual information PMI). We will also use additional linguistic models to account for more subtle language complexities and nuance such as parts of speech, and disambiguated words. We will use automated computational methods (e.g., deep learning-based object recognition) combined with manual coding to classify features (e.g., healthy or unhealthy food, physical activity, smoking, and drinking) in images. To determine nutritional content of food images, for example, we will use the imagga.com image classification software, combined with analysis of the words used in the text associated with images to recognize food images. Those images that are food images will then, to the best of our ability, be compared to a list of healthy and unhealthy groupings (e.g. high salt, high fat) and also compared to a USDA database of precise nutritional values for over 30 nutrients for 8600 food items. We will also construct a convolutional neural network based on labeled food and health behavior-related images to train a model to recognize images in the most frequent categories which our first pass fails to find. We will analyze the labeled images to better understand the nature of food posting, and how they vary with the time of day, demographics of the person posting the image. We will compare summary data from smartphones with self-reported data. Time series data from sensors will be used to analyze presumed changes in behavior using a previously validated health behavior activity change detection framework which segments time series data by time periods, identifies changes and their significance, and identifies the presumed locus of changes. The strength of using different types of data (text, images, sensors) is that each provides a unique type of information. Sensors provide direct measurements of protective and risk factors for CV, but they only measure what they are intended to measure. On the other hand, text and image data have been shown to capture a wide variety of information about people from demographics and personality to mood and beliefs. Further, each patient may use differing proportions of each modality such that, for example, text may make up for a lack of images and vice-versa. As digital media data may over-represent, under-represent or not represent health behaviors we will compare survey data and clinical data with digital data to quantify differences in behaviors and risk factors. We will explore statistical and machine learning methods for combining heterogeneous variables into predictive models. For our main analysis, we will both explore the correlations between the different modalities to better understand when they provide redundant or non-redundant information and we will, more importantly, combine the different modalities into a single predictive model. Standard machine learning methods such as random forests make it easy to add heterogeneous features to a single predictive model, and give measures of variable significance' indicating how much each feature contributes to predictive accuracy. We will also test more sophisticated machine learning methods for combining multiple modalities in a single model, such as using extensions of the 'elastic net' regression and dimensionality reduction framework that account for the fact that different modalities require different regularization penalties. We will also explore imputation and "back-off" methods that account for the fact that different patients will have substantially different amounts of data available in different modalities. These methods work by either estimating ("imputing") values for the missing data or automatically adjusting the weights given to different modalities for each patient based on the amount of data available for that patient. For Objective 1: Sample characterization: We will use summary statistics to describe patient demographics, survey response data, and digital data usage (e.g. frequency of posting, number of social media platforms). Descriptive data will be presented as mean (SD) for continuous variables and frequencies of participants for categorical variables. 5b Extracting topics and features: We will use the Mallet package for implementation of the Latent Dirichlet Allocation (LDA) method for clustering language data of all participants. The LDA probabilistic model assumes that documents (e.g. Facebook status updates) contain a distribution of topics which then contain a distribution of words. Ultimately, words are grouped together by considering the other words they appear with. Descriptive statistics, t-tests (continuous measures) and chi-squared tests (categorical measures) will be used to compare topics and

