
food images. Those images that are food images will then, to the best of our ability, be compared to a list of healthy and unhealthy

groupings (e.g. high salt, high fat) and also compared to a USDA database of precise nutritional values for over 30 nutrients for 8600 food items. We will also construct a convolutional neural network based on labeled food and health behavior-related images to train a model to recognize images in the most frequent categories which our first pass fails to find. We will analyze the labeled images to better understand the nature of food posting, and how they vary with the time of day, demographics of the person posting the image. We will compare summary data from smartphones with self-reported data. Time series data from sensors will be used to analyze presumed changes in behavior using a previously validated health behavior activity change detection framework which segments time series data by time periods, identifies changes and their significance, and identifies the presumed locus of changes. The strength of using different types of data (text, images, sensors) is that each provides a unique type of information. Sensors provide direct measurements of protective and risk factors for CV, but they only measure what they are intended to measure. On the other hand, text and image data have been shown to capture a wide variety of information about people from demographics and personality to mood and beliefs. Further, each patient may use differing proportions of each modality such that, for example, text may make up for a lack of images and vice-versa. As digital media data may over-represent, under-represent or not represent health behaviors we will compare survey data and clinical data with digital data to quantify differences in behaviors and risk factors. We will explore statistical and machine learning methods for combining heterogeneous variables into predictive models. For our main analysis, we will both explore the correlations between the different modalities to better understand when they provide redundant or non-redundant information and we will, more importantly, combine the different modalities into a single predictive model. Standard machine learning methods such as random forests make it easy to add heterogeneous features to a single predictive model, and give measures of variable significance indicating how much each feature contributes to predictive accuracy. We will also test more sophisticated machine learning methods for combining multiple modalities in a single model, such as using extensions of the 'elastic net' regression and dimensionality reduction framework that account for the fact that different modalities require different regularization penalties. We will also explore imputation and "back-off" methods that account for the fact that different patients will have substantially different amounts of data available in different modalities. These methods work by either estimating ("imputing") values for the missing data or automatically adjusting the weights given to different modalities for each patient based on the amount of data available for that patient. For Objective 1: Sample characterization: We will use

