
summary statistics to describe patient demographics, survey response data, and digital data usage (e.g. frequency of posting, number of social media platforms). Descriptive data will be presented as mean (SD) for continuous variables and frequencies of participants for categorical variables. 5b Extracting topics and features: We will use the Mallet package for implementation of the Latent Dirichlet Allocation (LDA) method for clustering language data of all participants. The LDA probabilistic model assumes that documents (e.g. Facebook status updates) contain a distribution of topics which then contain a distribution of words. Ultimately, words are grouped together by considering the other words they appear with. Descriptive statistics, t-tests (continuous measures) and chi-squared tests (categorical measures) will be used to compare topics and features with survey data. For example, NHANES survey questions (e.g. Do you now smoke cigarettes?) would be compared with images of cigarette smoking. For Objective 2: We will compare prediction models with and without digital variables. Probability weighted Cox proportional hazard analysis with robust variance estimates will be used to assess the association between each variable from digital media and CHD in univariable and multivariable models. We will use graphical and analytical methods to test the proportional hazards assumption for each analysis. To evaluate the predictive strength of digital data, we will build four predictive machine learning models using a stepwise sequence to select the most parsimonious model using combinations of risk factors. (1. Framingham predictors / American College of Cardiology ASCVD Risk Estimator Plus alone, 2. Framingham predictors / American College of Cardiology ASCVD Risk Estimator Plus + SES, 3. Framingham predictors / American College of Cardiology ASCVD Risk Estimator Plus + digital topics/ features, 4. Framingham predictors / American College of Cardiology ASCVD Risk Estimator Plus + digital topics/features+ SES) For Objective 3: We will use Super Learner, the ensemble machine learning approach which allows for the specification of multiple plausible candidate prediction models. Each of the candidate models is applied to a training set and outcomes are predicted using the validation set. A loss function is calculated within each validation set and then averaged across validation sets, which provides the estimated cross-validated risk score for each method. Calibration will be assessed using a calibration plot comparing the predicted probabilities (obtained using fixed regression coefficients of the prediction models) with the observed probabilities. The Super Learner algorithm finds the optimal weighted combination across all of the specified methods. Van der Laan et al. proved the asymptotic efficiency of the Super Learner algorithm and demonstrated that the optimal combination performs at least as well as the best estimators from the candidate models. We will implement Super Learner in R (The R Foundation for Statistical Computing). In this approach generalized estimating equation (GEE) and generalized linear mixed effects models will be explored to account for repeated measures per patient over time. One of the challenges of cost analyses is censoring, since cost may be incomplete and available for

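### Objective 1 names no test for a graded topic or feature against a graded survey answer; t-tests and chi-squared tests fit such pairs only by grouping one side or ignoring order

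*SAP*

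**What the plan says.** The SAP (Final Analysis Plan, Objective 1, on extracting topics and features) gives the method in one sentence: "Descriptive statistics, t-tests (continuous measures) and chi-squared tests (categorical measures) will be used to compare topics and features with survey data". The Protocol's Analysis Plan repeats it. The one example follows: "For example, NHANES survey questions (e.g. Do you now smoke cigarettes?) would be compared with images of cigarette smoking".

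The Protocol's account of the study instruments lists the survey content, including "NHANES: SES [income, education], diet behavior and nutrition, physical activity and physical fitness, smoking and tobacco use". The digital side is described in the SAP as topic distributions from Latent Dirichlet Allocation and usage measures such as posting frequency and number of platforms. It also includes classifier labels and image categories.

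Other parts of the SAP might seem to cover the comparison but do not:

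- Correlations are planned among the digital sources: "we will both explore the correlations between the different modalities to better understand when they provide redundant or non-redundant information".
- A further comparison is promised without a method: "we will compare survey data and clinical data with digital data to quantify differences in behaviors and risk factors".
- Regression, adjusted for demographics, relates latent classes of platform use to health status, perceptions and activation. It does not relate topics to the baseline survey.
- The Cox models of Objective 2 concern CHD.

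Neither document states an alpha, effect size, power, cut-point or rule for multi-level answers for this comparison.

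**The concern.** A t-test compares a measure between two groups. A chi-squared test treats categories as unordered. Neither relates a graded quantity on one side to a graded quantity on the other. Topic proportions and posting frequency are graded. Income, education, diet and physical activity are by nature ordered or continuous. For those pairs the analyst must group the feature, group the survey answer, or tabulate levels without regard to their order.

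Two things are at stake. Power falls, so modest true associations between digital features and risk factors may be missed. Any cut-point is also left to the analyst, and the choice can change which topics are reported as associated. Objective 1 aims to find features related to CHD and its risk factors, and the open-vocabulary methods will generate many candidates.

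**Working it through.** The plan has no power figure for this comparison, so there is nothing to reproduce. The size of the loss has to be worked out under assumptions.

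**Inputs**

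- N = 1000, from the Protocol (Study duration): "We aim to recruit 1000 participants over 4 years". This is a recruitment target. The number with usable text or images is not stated, so N = 500 is shown as well.
- Assumed: two-sided alpha 0.05; true correlation r from 0.05 to 0.20; jointly normal underlying variables; cuts at 50/50 or 80/20; five survey levels of equal size.

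**Formulas**

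1. Full scale: z = atanh(r) × √(N − 3); power = Φ(z − 1.96) + Φ(−z − 1.96).
2. One side cut at proportion p, then a t-test: replace r by r × φ(z_p)/√(p(1 − p)). The factor is 0.798 at 50/50 and 0.700 at 80/20. Squared, these are 0.64 and 0.49, the share of information kept.
3. Both sides halved, 2×2 chi-squared: phi coefficient = (2/π) × arcsin(r); non-centrality N × phi², 1 degree of freedom.
4. Five survey levels by a halved feature, 5×2 chi-squared: cell probabilities from the bivariate normal, 4 degrees of freedom.

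**Numbers at N = 1000, r = 0.10**

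- Full scale: 0.1003 × √997 = 3.168; Φ(1.208) = 88.7%.
- Median-split t-test: r becomes 0.0798, z = 2.525; Φ(0.565) = 71.4%.
- 80/20 t-test: r becomes 0.0700, z = 2.214; Φ(0.254) = 60.0%.
- 2×2 chi-squared: phi = 0.0638, non-centrality 4.07; power 52.3%.
- 5×2 chi-squared: non-centrality 5.72; power 45.0%.

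**Power over the range (points lost against the full scale in brackets)**

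| N | r | Full scale | Median-split t | 80/20 t | 2×2 chi-squared | 5×2 chi-squared |
|---|---|---|---|---|---|---|
| 1000 | 0.05 | 35.2% | 24.3% (10.9) | 19.7% (15.5) | 17.2% (18.0) | 13.3% (22.0) |
| 1000 | 0.08 | 71.6% | 52.3% (19.3) | 42.5% (29.1) | 36.4% (35.2) | 29.4% (42.2) |
| 1000 | 0.10 | 88.7% | 71.4% (17.3) | 60.0% (28.6) | 52.3% (36.4) | 45.0% (43.7) |
| 1000 | 0.15 | 99.8% | 96.7% (3.1) | 91.4% (8.3) | 85.8% (14.0) | 83.4% (16.4) |
| 1000 | 0.20 | 100% | 99.9% (0.1) | 99.4% (0.6) | 98.2% (1.8) | 98.3% (1.7) |
| 500 | 0.10 | 60.9% | 43.0% (17.9) | 34.6% (26.3) | 29.7% (31.2) | 23.4% (37.5) |

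**Check by simulation** (five-level survey item, N = 1000, 4000 runs per scenario)

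| r | Trend test on ordered levels | t-test after a 60/40 collapse | 5×2 chi-squared |
|---|---|---|---|
| 0.08 | 67.0% | 52.5% (14.5) | 29.0% (38.0) |
| 0.10 | 85.7% | 70.4% (15.3) | 44.1% (41.6) |

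At r of 0.08 to 0.10 and N = 1000, near-even t-test splits therefore cost about 14 to 19 points, and chi-squared tests with the feature grouped about 35 to 44.

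**The case against.** A reader might infer that the survey answers have to be cut, and that a large loss of power follows in every case. The documents support neither reading.

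- A t-test can keep the full survey score and compare it between two feature groups. A chi-squared test can keep every income or education level. The survey side need not be the one that is grouped.
- Many planned features are labels already: active or sedentary, healthy or unhealthy food, smoking in an image. Where such a feature is present or absent per participant, nothing is lost. In a simulation of a two-level feature against an uncollapsed five-level score (N of 500 and 1000, latent r of 0.10 to 0.20, prevalence 20% and 50%), t-test and Spearman power differed by at most 1.5 points.
- The plan describes no median split. The larger losses come from a chi-squared test on a grouped continuous feature, a use the SAP does not spell out, since it assigns continuous measures to t-tests.
- The survey items are attached to the application and are not in the text reviewed. That the domains are graded is inferred from their names.
- The topic part of the first hypothesis compares patients with and without heart disease, a natural two-group contrast. The documents do not call the survey comparison the main screen of features.

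All of this stands, and it limits the point to pairs in which both sides are graded. It does not remove the gap. For those pairs the two named tests are the only inferential methods given, and neither uses both scales in full.

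**Conclusion.** The point holds for graded features against ordered or continuous survey answers, and only there. As written, such a pair can be tested only by grouping one side or discarding order. The size depends on assumed values. The range of 14 to 19 points (near-even t-test split) and 35 to 44 points (grouped chi-squared) belongs to r of 0.08 to 0.10 at N = 1000, two-sided 5%, with near-normal variables. It is not a general figure: a median-split t-test loses about 3 points at r = 0.15 and almost nothing at r = 0.20, while an uneven cut loses more than a median split. The real effect sizes and the analysable number per feature are unknown. This is a cheap gain in efficiency and clarity; the named tests are not invalid.

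**What to change.** Amend the sentence in the SAP and its twin in the Protocol's Analysis Plan:

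- Keep the t-test and chi-squared test for survey items or features that are truly two-level or unordered.
- Where both the feature and the survey measure are ordered or continuous, use Spearman correlation, linear or proportional-odds regression, or a trend test, on one value per participant.
- State that neither side is collapsed for the association test. Grouped summaries may still be shown descriptively.

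The cost is one sentence in each document and no new data. A coefficient is slightly harder to read than a difference between two groups, and the monotone or linear form has to be checked.

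### Objective 1 compares digital features with survey answers by t-tests and chi-squared tests without stating a unit of analysis, a volume denominator or any allowance for many posts or images per person

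*SAP*

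**What the plan says.** Under Objective 1 of the SAP's Final Analysis Plan (repeated in the Protocol's Analysis Plan), the methods named for setting digital features against survey answers are descriptive statistics and two tests: "t-tests (continuous measures) and chi-squared tests (categorical measures) will be used to compare topics and features with survey data". The single example is an NHANES question on current smoking, which "would be compared with images of cigarette smoking".

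The digital data arrive many per person. In the topic model, "documents (e.g. Facebook status updates) contain a distribution of topics which then contain a distribution of words". Features such as smoking or food type are classified in images. Facebook and Instagram users must be willing to share past data plus 60 days of prospective data (Protocol, Key inclusion criteria). No step from posts or images to one value per participant is given. A separate sentence reads "We will analyze the labeled images to better understand the nature of food posting, and how they vary with the time of day", and adds the demographics of the person posting. It names no test.

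The SAP expects that "different patients will have substantially different amounts of data available in different modalities". One response is "automatically adjusting the weights given to different modalities for each patient based on the amount of data available for that patient", but this is to be explored for the models that combine modalities. Robust variance is named for the Objective 2 Cox models. Under Objective 3, GEE and "generalized linear mixed effects models will be explored to account for repeated measures per patient over time". Nothing comparable is attached to Objective 1, where posting frequency appears only as a descriptive variable.

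**The concern.** Both named tests assume independent observations. A survey answer exists once per person, while posts and images exist many times per person and in very unequal numbers. The plan's example pairs a yes/no question with images, so a chi-squared test is the obvious choice, and it can be built in two ways.

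- **Image as the unit.** Images from one person resemble each other, so the test overstates the information and heavy posters dominate.
- **Person as the unit, scored as any cigarette image.** Independence holds, but the chance of a positive score rises with the number of images shared, whatever the behaviour. If smokers and non-smokers post different amounts, the test picks up volume.

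The second route needs a link between volume and survey answer. The documents give no figure for one, but H1 (Protocol, Primary outcome variable(s)) expects phenotypes built partly on quantity of posting to be associated with health status, so such a link is plausible on the study's own reasoning.

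Topics and features are the primary outcome for Objective 1. An unstated unit leaves the choice between a valid test and a badly inflated one open until the data are seen.

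**Working it through.** The documents give no alpha, power, effect size or sample-size calculation for Objective 1, so there is no planned figure to reproduce. Only the 1000 participants come from the documents (the Protocol's recruitment target). Every other input is an assumption.

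**1. Image or post as the unit: formula.** With mean m items per person, coefficient of variation CV and within-person correlation ICC, the variance inflation is

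DEFF = 1 + ((1 + CV²)·m − 1)·ICC,

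and the true type I error of a nominal two-sided 0.05 test is 2·(1 − Φ(1.96/√DEFF)).

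For m = 50, CV = 1, ICC = 0.05: DEFF = 1 + (2·50 − 1)·0.05 = 5.95 and √5.95 = 2.44. Then 1.96/2.44 = 0.80, giving a type I error of 0.42. Simulation at these values (2% of items positive, equal volume) also gave 0.42. Over m = 10 to 200, CV = 0 to 2 and ICC = 0.01 to 0.10, DEFF runs from 1.09 to 100.9 and type I error from 0.06 to 0.85.

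**2. Why any-image scoring depends on volume.** If 1% of everyone's images are positive, the chance of at least one positive among m images is 1 − 0.99^m. That is 10% for m = 10, 39% for m = 50 and 87% for m = 200, with identical behaviour.

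**3. Null simulation of the smoking example.** Assumptions: 1000 people, 30% in one survey group, 2% of images positive in both groups, median 20 to 100 images per person (lognormal, log-SD 1.0), and a beta-binomial with within-person correlation 0.02 to 0.10. Rejection rates at nominal 0.05:

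| Analysis | Type I error |
|---|---|
| Chi-squared on images | 21–79% |
| Chi-squared on any image, equal volume | about 5% (4–7%) |
| Chi-squared on any image, 1.25-fold volume gap | 9–26% |
| Chi-squared on any image, 1.5-fold volume gap | 25–65% |
| Per-person proportion, or participant-clustered rate | 2–8% |

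The ends of these ranges carry Monte Carlo error. A repeat with 1000 replicates per setting gave 23–79% for the image-level test, 8–29% and 20–64% for the any-image test at the two volume gaps, and 3–7% for the last row.

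**4. A second set of assumptions.** Here 20% answer yes, mean posts are 50 (CV 1) or 100 (CV 2), and the feature rate is 1%, 2% or 10% with ICC 0.02, 0.05 or 0.10. The any-item chi-squared test rejected in 4.5–5.6% of runs with equal volume, 14–16% at a 1.25-fold gap and 33–45% at a 1.5-fold gap. A t-test on raw counts rejected in 4–6%, 17–42% and 37–87%. A t-test on each person's proportion stayed at 3.4–5.3% (Welch version 3.9–6.1%) in every setting, including the 1.5-fold gap.

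**The case against.** The strongest reply is that the SAP never says posts or images will be tested as independent observations. The status update is offered as an example of a document for fitting the topic model, which does not fix the unit of the later test. Several cues point to the person: survey answers are per person, a unique code links each participant's survey to their posts, H1 contrasts patients with and without heart disease, and the descriptive summary counts participants. An ordinary t-test on one proportion or mean per person fits the SAP sentence as written and keeps its level. Posting volume is also an input to the latent class analysis, and the study is described as correlational.

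Much of this stands. A reader might infer that any unit of analysis produces false associations. That is not supported: one proportion per person is valid, and unequal volume alone does no harm at person level. Harm needs a summary that grows with volume, together with a volume difference between survey groups. A reader might also infer that p-values and intervals for the food-image analysis by time of day and demographics are wrong. The SAP promises none for it.

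The reply does not remove the gap. The person-level cues sit outside the sentence naming the tests. The back-off weights belong to the predictive models, and entering volume into the latent classes does nothing for the chi-squared comparison. Time of day is a property of the image, so any inference on it would involve repeated images per person.

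**Conclusion.** The point holds as an omission with a concrete consequence. For Objective 1 the SAP states no unit, no volume denominator and no method for repeated items per person, and the two natural chi-squared versions of its own example can mislead. Results from these comparisons may be wrong, depending on a choice not yet written down; the documents do not show that they will be.

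For image-level testing, the size rests on assumed image counts and within-person correlation. At few items and low correlation the inflation is slight (0.06 at m = 10, CV = 0, ICC = 0.01); at moderate values it is severe. For any-image scoring it rests further on a volume gap between survey groups, which H1 makes plausible but no document quantifies. Without a gap, that test holds its level.

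**What to change.** In the Objective 1 section of the SAP:

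- Replace the chi-squared comparison of image features with a per-participant rate, the number positive out of the number shared, compared between survey groups by t-test. Alternatively, use a binomial GEE or mixed model clustered on participant. Name the choice in advance.
- For topics, use each person's mean over their posts, with a stated minimum amount of text.
- For any inference on food images by time of day or demographics, use the participant-clustered model.

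This is a wording change that needs no new data, and the clustered methods are already named for Objective 3. The costs are wider intervals than an image-level analysis would show, and the loss from the topic tests of people with very little text.
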